1.0 SYNOPSIS

Title:	Advanced Bradycardia Device Feature Utilization and Clinical Outcomes II
Acronym:	BRADYCARE II
Purpose:	To characterize the utilization of diagnostic capabilities in SJM pacemakers to manage patients with a standard bradycardia pacing indication
Objectives:	 The primary objective of the study is to characterize: Complication rates in the general pacemaker patient population The secondary objectives of the study are to characterize: Impact of the usage of advanced features in pacemaker on the clinical outcomes MRI scanning capabilities and rates in pacemaker patients by country
Outcome Measures:	 The primary outcome measure is: Complication rate at 1 year post implant in general pacemaker population The secondary outcome measures are: Effect of the usage of advanced features in pacemaker on clinical outcomes Number and proportion of MRI scans received in pacemaker patients by country
Design:	The study is a prospective, non-randomized, multi-center observational study designed to evaluate the diagnostic capabilities, indications, MRI scanning capabilities and clinical outcomes of patients implanted with SJM pacemakers. The total duration of the study is expected to be approximately 30 months. The clinical study will be conducted in up to 160 centers across Europe, Middle East, Africa, (EMEA region) and Asia, Australia and New Zealand (Asia-Pac region). Up to 2016 subjects will be enrolled in this study. Subjects will be followed for 1 year after pacemaker implant.
Devices used:	SJM Assurity MRI [™] , Endurity MRI [™] or other SJM MRI compatible pacemakers in EMEA region and the Asia-Pac region will use an SJM Accent MRI [™] , Assurity MRI [™] , Endurity MRI [™] or other SJM MRI compatible pacemakers.

Study Name: BRADYCARE II

CIP

[figure not shown]
Study Population:	A patient becomes a subject once he/she has been fully informed about the study, has agreed to participate, signed & dated the consent.
	Patients who have been implanted with an SJM Assurity MRI [™] , Endurity MRI [™] or other SJM MRI compatible pacemakers in the EMEA region within 30 days or patients implanted with an Accent MRI [™] , Assurity MRI [™] , Endurity MRI [™] or other SJM MRI compatible pacemakers in the Asia-Pac region within 30 days.
Inclusion/Exclusion	Inclusion Criteria
Criteria:	 Patients who have been implanted with an SJM Assurity MRI[™], Endurity MRI[™] or other SJM MRI compatible pacemakers in the EMEA region within 30 days or patients implanted with an Accent MRI[™], Assurity MRI[™], Endurity MRI[™] or other SJM MRI compatible pacemakers in the Asia-Pac region within 30 days. Patient is geographically stable and willing to comply with the required follow-up schedule. Patient is not pregnant or planning to become pregnant during the course of the study. Patient is > 18 years of age. Exclusion Criteria Patient's life expectancy is less than 1 year.
Data Collection:	Enrollment (within 30 days of implant)
Data Concellon.	Device indication, Device information, Medical history, Current drug
	therapy, Export device data.
	6-Month Post Implant Visit (+3 months) MRI (yes/no), Export device data.
	12-Month Post Implant Visit (±2 months)
	MRI (yes/no), Export device data.
	Unscheduled Office Visits
	MRI (yes/no), Export device data (if available), Hospitalizations.

Study Name: BRADYCARE II

CIP

1.1 Study Flow Chart

Patients implanted with an SJM Assurity MRI[™], Endurity MRI[™] or other SJM MRI compatible pacemaker in the EMEA region or patients implanted with an Accent MRI™, Assurity MRI™, Endurity MRI™ or other SJM MRI compatible pacemaker in the Asia-Pac region.

Ver. A

Study Name: BRADYCARE II

CIP

2.0 BACKGROUND AND JUSTIFICATION FOR CLINICAL STUDY

Pacemaker technology is constantly evolving. In the past 10 years, numerous advancements have been made in pacemaker therapy, diagnostics and connectivity. These advancements include automated capture, automated sensing, patient alert functions, algorithms minimizing ventricular pacing, automatic mode switching in response to atrial tachyarrhythmia, rate responsive pacing, advanced diagnostic features, remote monitoring and radiofrequency (RF) technology. However, little information is available on how these new features are being utilized by physicians in the real world, especially in countries outside the USA, and how these features impact patient outcomes. ³⁻⁸

Many patients who receive pacemakers will go through natural changes in their disease state and lifestyle that may warrant changes in the way their pacemaker is programmed. St. Jude Medical pacemakers have the ability to identify clinical arrhythmias and provide a wide variety of programming options to address changing clinical status.

This observational study is designed to gain a better understanding of how diagnostic capabilities in the Accent MRI[™], Assurity MRI[™], Endurity MRI[™], or other St. Jude Medical MRI compatible pacemakers are being utilized to manage patients. Pacemaker information and health status will be collected for all patients enrolled in this study. The insight obtained from the device and clinical data collected in this study could lead to potential improvements in device parameter nominal settings. Furthermore, through this study, new insights may be obtained about the progression of heart disease in bradycardia patients and how the flexibility of programming and diagnostic capabilities can benefit the changing clinical status of these patients.

The Advanced Bradycardia Device Feature Utilization and Clinical Outcomes II (BRADYCARE II) study is sponsored by St. Jude Medical (hereinafter referred to as SJM) and will include only market approved products.

Study Name: BRADYCARE II

CIP

3.0 RISKS AND BENEFITS OF THE CLINICAL STUDY

The risks associated with the use of an MRI compatible pacemaker are anticipated to be comparable to those associated with the use of other currently available pacemakers. Subjects participating in this study are indicated for a pacemaker system as part of their standard medical management and are subject to the risks associated with these devices.

3.1 Description of Subject Population

The study population includes those subjects who meet a standard bradycardia pacing indication, are implanted with an SJM Assurity MRI[™], Endurity MRI[™] pacemaker or similar model in the EMEA region and patients implanted with an SJM Accent MRI, Assurity MRI, Endurity MRI or similar model in the Asia-Pac region, and meet inclusion/exclusion criteria. For the SJM BRADYCARE II study, it is the sponsor's intention that the enrolled subject population be as representative as possible of the eligible population. Physician investigators are strongly encouraged to evaluate all consecutive eligible subjects for participation in the study and, if inclusion and exclusion criteria are met, to approach all eligible subjects. The minimum enrollment requirement for completing this study is 2016 subjects.

The study will be conducted at up to 160 centers across countries in Europe, Middle East, Africa (EMEA region) and Asia, Australia and New Zealand (Asia-Pac region). Centers will be selected for participation in the study based on their ability to screen and enroll eligible subjects, and perform the required study procedures. SJM will attempt to have a diverse group of centers participating in the study including academic and non-academic institutions. A maximum of 200 of the total enrollment can be included per center.

3.2 Anticipated Clinical Benefits

The information gathered in this study will add to the understanding of treatment options for subjects with slow heart rates who require MRI scans. SJM expects subjects implanted with an SJM Brady MRI pacemaker system to receive the same benefit as subjects implanted with other SJM pacemaker systems.

4.0 STUDY DESIGN

4.1 Purpose

The purpose of this observational study is to characterize the utilization of diagnostic capabilities in SJM pacemakers to manage patients with a standard bradycardia pacing indication. Subjects will be followed for 1 year (12 months). It is estimated this study will last approximately 2.5 years (30 months) inclusive of the enrollment period.

4.2 Study Design and Scope

The study is a prospective, non-randomized, multi-center observational study designed to evaluate the diagnostic capabilities, indications, MRI scanning capabilities and clinical outcomes of patients implanted with an MRI compatible SJM pacemaker with a standard bradycardia pacing indication. Any patient that receives an Assurity MRI, Endurity MRI pacemaker (or

Template 90153521 Ver B Page 10 of 38

Study Name: BRADYCARE II

CIP

newer version) in the EMEA region or any patient that receives an Accent MRI, Assurity MRI, Endurity MRI or similar SJM MRI compatible device in the Asia-Pac region is eligible for enrollment in the study if they meet the inclusion/exclusion criteria.

Subjects will be followed for 12-months after pacemaker implant. Data will be collected at enrollment (within 30 days of device implant), 6 and 12-months post-implant and during any unscheduled follow-up visit. Remote follow-up using Merlin@home® and Merlin.net® is allowed for the 6-month visit as per the site's standard of care. However, subjects must have an in-office follow-up visit at 12-months post pacemaker implant. During the follow-up visits, arrhythmic episode diagnoses, device data, drug therapy, stored electrograms and if an MRI was done will be collected. All clinical events such as hospitalizations, emergency room visits, system revisions and external cardioversions will also be collected. All study data, including device data and stored electrograms will be sent to SJM via the electronic data capture (EDC) system.

This study will be offered to all subjects who are implanted with an SJM Brady MRI system in the EMEA and Asia-Pac region, therefore, the study population is expected to reflect the population of patients implanted with an SJM Brady MRI system in the EMEA and Asia-Pac region.

4.3 Number of Subjects Required to be Included in the Study

Up to 2016 subjects will be enrolled in this study. No more than 200 enrollments (10% of the total study enrollment) will be allowed per center without prior SJM approval.

4.4 Estimated Time Needed to Enroll this Subject Population

The study may continue up to 2.5 years (30 months), dependent on the rate of enrollment.

4.5 Objectives

4.5.1 Objectives

The primary objective of the study is to characterize:

• complication rates in the general pacemaker patient population

The secondary objectives of the study are to characterize:

- Impact of usage of advanced features in pacemaker on the clinical outcomes
- MRI scanning capabilities and rates in pacemaker patients by country

4.5.2 Outcome Measures

The primary outcome measure is:

• Complication rate at 1 year post implant in general pacemaker population

Study Name: BRADYCARE II

CIP

The secondary outcome measures are:

- Effect of the usage of advanced features in pacemaker on the clinical outcomes
- Number and proportion of MRI scans received in pacemaker patients by country

4.6 Inclusion and Exclusion Criteria

A subject, who meets all of the inclusion criteria, and none of the exclusion criteria, is eligible to participate in this study.

All subjects enrolled in the clinical study (including those withdrawn from the clinical study or lost to follow-up) will be accounted for and documented, assigning an identification code linked to their names, alternative identification or contact information.

This log will be kept up to date throughout the clinical study by the principal investigator or his/her authorized designee. To ensure subject privacy and confidentiality of data, this log must be maintained throughout the clinical study at the clinical site.

To participate in this clinical study, the subject must meet all of the following inclusion criteria:

4.6.1 Inclusion Criteria

- Patients who have been implanted with an SJM Assurity MRI[™], Endurity MRI[™] or other SJM MRI compatible pacemakers in the EMEA region within 30 days or patients implanted with an Accent MRI[™], Assurity MRI[™], Endurity MRI[™] or other SJM MRI compatible pacemakers in the Asia-Pac region within 30 days.
- Patient is geographically stable and willing to comply with the required follow-up schedule.
- Patient is not pregnant or planning to become pregnant.
- Patient is > 18 years of age.

Subjects are not eligible for clinical study participation if they meet the following exclusion criteria:

4.6.2 Exclusion Criteria

• Patient's life expectancy is less than 1 year.

Ver. A

Study Name: BRADYCARE II

CIP

4.7 Subject Population

The study population consists of subjects who have been implanted with a SJM bradycardia pacemaker system.

4.7.1 Subject Screening

All subjects presenting at the investigational site should be screened by a member of the investigational team previously trained on the CIP and delegated to do so.

Subjects who do not meet the inclusion/exclusion criteria will not be eligible to participate in this study.

Subjects meeting the inclusion/exclusion criteria will be fully informed about the study and asked to participate in the study. If the subject agrees to participate, a duly signed and dated subject Informed Consent will be obtained.

4.7.2 Point of Enrollment

Subjects are considered enrolled in the study from the moment the subject has provided written Patient Informed Consent. (Refer to section 4.8 for the Informed Consent Process).

4.8 Informed Consent Process

4.8.1 General Process

Prior to enrolling in the clinical study and conducting study-specific procedures, all subjects will be consented, as required by applicable regulations. The consent form must be signed and dated by the subject and by the person obtaining the consent.

The principal investigator or his/her authorized designee will conduct the Informed Consent Process. This process will include a verbal discussion with the subject on all aspects of the clinical study relevant to the subject's decision to participate in the clinical study.

The subject shall be provided with the informed consent form that is written in a language that is understandable to the subject and has been approved by the center's Ethics Committee. Failure to obtain informed consent from a subject prior to study enrollment should be reported to St. Jude Medical within 5 working days and to the reviewing center's Ethics Committee consistent with the center's Ethics Committee reporting requirements.

Study Name: BRADYCARE II

Ver. A

CIP

5.0 DEVICE

5.1 Device Description

In this observational study, subjects are already implanted with an approved St. Jude Medical Brady MRI pacemaker including Accent MRI[™], Assurity MRI[™], Endurity MRI[™] or other SJM MRI compatible pacemaker.

The MRI pacemaker has new hardware and firmware to prevent unintended stimulation due to electromagnetic fields created by the MRI scanner. The new hardware and firmware include:

- Reduction in feed-through capacitance to mitigate gradient-induced stimulation
- Addition of a band-stop filter (MR filter assembly) to limit the ingress of MRI-specific frequencies which otherwise could result in RF rectification and/or other interference.

The device shape and size is modified to accommodate the MRI filter assembly.

The intended purpose of a SJM Brady MRI System, instructions for use, storage and handling instructions, preparation for use and precautions can be found in the instructions for use for each component (IFUs). Use of a SJM Brady MRI System should follow a standard bradycardia pacing indication (also provided in the IFU).

The SJM Brady MRI System has been market released and may be used by any physician experienced with implanting standard pacemakers and leads. No special training is needed to use the device. All medical and surgical procedures will be followed as instructed in the IFU.

Investigational Device Model/Type or Market Component Released Accent MRI[™] (PM1124, PM1224, PM2124, PM2224) **Pacemakers** Market Released Assurity MRITM (PM1272, PM2272) Market Released Endurity MRITM (PM1172, PM2172) Market Released Endurity MRITM Conditional (PM1162, PM2162) Market Released Endurity Core (PM1140, PM2140, PM1152, PM2152) Market Released

Table 1: Description of Proposed Devices

5.2 Device Accountability (if applicable)

Device accountability is not required for this study.

5.3 Device Handling & Storage

St. Jude Medical requires all products be stored, according to the IFU.

Study Name: BRADYCARE II

[figure not shown]
Ver. A

CIP

6.0 PROCEDURES

6.1 Study Flow Chart

Patients implanted with an SJM Assurity MRI[™], Endurity MRI[™] or other SJM MRI compatible pacemaker in the EMEA region or patients implanted with an Accent MRI[™], Assurity MRI[™], Endurity MRI[™] or other SJM MRI compatible pacemaker in the Asia-Pac region.

Study Name: BRADYCARE II

Ver. A

CIP

6.2 Procedures

The clinical study will be conducted in accordance with the CIP. All parties participating in the conduct of the clinical study will be qualified by education, training, or experience to perform their tasks and this training will be documented appropriately.

The clinical study will not commence until St. Jude Medical receives written approval from the Ethics Committee and relevant regulatory authorities as applicable and all required documents have been collected from the site(s).

Table 2: List of all Study Specific Activities/Procedures

Visit Study Activity	Enrollment (within 30 days of implant)*	6-Month ^a (+/- 3 Months)	12-Month (+/- 2 Months)	Unscheduled Office Visit
Informed Consent Process	X			
Demographics	X			
Medical History	X			
Implant Indication	X			
System Information	X			
Drug Therapy	X			
Device Interrogation	X	X	X	(X)
Check if an MRI done	V	V	v	V
since the last visit (Yes/No)	X	X	X	X
Adverse Event	(X)	(X)	(X)	(X)
System Revision		(X)	(X)	(X)
Product Out of Service		(X)	(X)	(X)
Deviation	(X)	(X)	(X)	(X)
Withdrawal	·	(X)	(X)	(X)
Hospitalization	(X)	(X)	(X)	(X)
Death		(X)	(X)	(X)

^{*}Enrollment may occur same day as implant

6.3 Enrollment Visit

The following enrollment activities are performed after the subject has been screened and must occur before any study procedure/visit.

• The principal investigator or delegated study personnel are responsible for screening all potential subjects to determine subject eligibility for the study.

⁽a) The subject who has a remote 6-month follow-up using Merlin.net® must be contacted by phone.

⁽X) If applicable

Study Name: BRADYCARE II

Ver. A

CIP

 Record enrollment information (name of the study, date of consent and inclusion/exclusion information) in the hospital records and complete and submit the Enrollment and Medical History form in a timely manner (recommended within 5 days).

 Notification of enrollment to the Sponsor will take place only when the Sponsor receives the Enrollment form.

NOTE: As soon as the subject signs the Patient Informed Consent, adverse events need to be reported according to the guidelines mentioned in Section 8.2.

If a subject does not meet all inclusion criteria or meets the exclusion criteria, the subject cannot participate in the study and cannot be enrolled.

Subject data including gender, age, cardiac disease history, cardiac drug therapy, arrhythmia history, smoking history, system information and indication for pacemaker implant will be collected.

Interrogate the device and obtain the following device measurements:

- RA and RV bipolar capture thresholds (if applicable)
- P- and R-wave sensing amplitudes (if applicable)
- RA and RV lead pacing impedance (if applicable)

Upload device session records including all stored IEGMs using the SJM EDC Portal device data upload utility.

Below is the required data that must be collected:

- Enrollment Form
- Medical History Form
- Cardiac Drug Therapy
- Cardiac History
- System Information
- Device Interrogation
- Adverse Event(s) (if applicable)
- Hospitalization (if applicable)

Subjects who meet the inclusion/exclusion requirements, sign an Ethics Committee approved informed consent, and have been implanted with a SJM Brady MRI pacemaker system will be considered for enrollment into the study. If a subject does not meet all inclusion criteria or meets the exclusion criteria, the subject cannot participate in the study and cannot be enrolled. The enrollment date for subjects in the study will be the date when the protocol defined enrollment procedures are completed. Refer to Section 4.7.2 for specific points of enrollment.

6.4 Scheduled Follow-up Visits – 6-Month (+/- 3 Mon) and 12-Month (+/- 2 Mon) Post Implant

Enrolled subjects will be seen at 6-Months (+/- 3 Months) and 12-Months (+/- 2 Months) post pacemaker implant. During these visits, the following evaluations and procedures will be performed:

• Follow Up Form

Study Name: BRADYCARE II

Ver. A

CIP

- Device Interrogation
- System Revision Form (if applicable)
- Product Out of Service Form (if applicable)
- Adverse Event Form(if applicable)
- Deviation Form (if applicable)
- Hospitalization Form (if applicable)
- Withdrawal Form (if applicable)
- Death Form (if applicable)

Submit the completed forms and upload device session records including all IEGMs using the SJM EDC Portal device data upload utility.

For a remote 6-Month follow-up visit: Prior to obtaining the first remote follow-up the site must ensure that the Merlin.net[®] PCN option to clear all diagnostics and EGMs is enabled. The site must also ensure the session record export option is enabled. A phone interview must be completed in order to collect the required data (information about adverse events, MRI or hospitalizations since enrolling).

6.5 Unscheduled Visits

An Unscheduled Visit is defined as any visit where an active study subject returns to the participating study site for medical care outside of a specified study visit. Examples of unscheduled visits may include subjects returning to the office for an adverse event, wound check and/or device programming change.

The visit should be documented by completing the Unscheduled Visit Form and any other applicable forms (Adverse Event, System Revision, Product Out of Service, Deviation, Hospitalization, Withdrawal and Death Form).

Submit the completed forms and upload device session records (if applicable) including all IEGMs using the SJM EDC Portal device data upload utility.

Following an Unscheduled visit, the subject should be seen for the next scheduled study visit within window.

6.6 Subject Study Completion

When the subject's participation in the clinical study has been completed, the subject will return to the medical care as per physician's recommendation.

6.7 Any Known or Foreseeable Factors that May Compromise the Outcome of the Clinical Study or the Interpretation of the Results

The purpose of this study is to characterize the utilization of diagnostic capabilities in SJM pacemakers to manage patients with a standard bradycardia pacing indication. This study will be offered to all subjects who are implanted with an SJM Brady MRI system in the EMEA and Asia-Pac region. There are no foreseeable factors that may compromise the outcome of this study.

Ver. A

Study Name: BRADYCARE II

CIP

The study is not expected to have higher than normal rates of attrition. Follow up compliance will be closely monitored to ensure these rates do not rise higher than expected.

6.8 Criteria and Procedures for Subject Withdrawal or Discontinuation

Subjects must be informed about their right to withdraw from the study at any time and for any reason without sanction, penalty or loss of benefits to which the subject is otherwise entitled and withdrawal from the study will not jeopardize their future medical care or relationship with the Investigator. Subjects will be asked to specify the reason for the termination, but have the right not to answer.

The Investigator may decide to withdraw a subject from the study at any time with reasonable rationale. The subject's future care will not be influenced by a decision, voluntary or otherwise, to withdraw from the study. All reasonable efforts should be made to retain the subject in the clinical study until completion of the study.

Reasons for subject's withdrawal include, but are not limited to:

- Subject refuses to continue participating in the study
- Subject does not meet the inclusion/exclusion criteria and does not require additional follow-up for safety reasons
- Subject is deceased (Complete Death Form)
- Subject's non-compliance
- Subject's participation is terminated by the PI or Investigator, although the subject consented, since participation is no longer medically appropriate
- Subject is 'lost to follow up': Subject does not adhere to the scheduled follow up visits but has not explicitly requested to be withdrawn from the clinical study. Site personnel should at all times make all reasonable efforts to locate and communicate with the subject in order to achieve subject compliance to the scheduled follow up visits:
 - 1. A subject will be considered 'Lost to Follow Up' after a minimum of two phone calls of a physician or delegate at the investigational site to the subject or contact. These two phone calls need to be documented in the subject's hospital records.
 - 2. If these attempts are unsuccessful, a certified letter should be sent to the subject's last known address or general practitioner (GP) and a copy of this letter should be maintained in the subject's hospital records.

Note: If a subject misses one or more of the scheduled follow up visits (inclusive of the assigned visit windows), this will be considered as a missed visit requiring submission of a Deviation Form. The subject may return for subsequent visits and will not be excluded from the study.

If a subject withdraws from the clinical study, the site will record the subject's reasons for withdrawal on a Withdrawal CRF.

When subject withdrawal from the clinical study is due to an adverse event the subject will be followed by their study doctor per standard of care outside of the study until the adverse event is resolved or the

Study Name: BRADYCARE II

Ver. A

CIP

PI determines that the subject's condition is stable. The status of the subject's condition should be documented at the time of withdrawal.

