8.1.6 Anticipated Serious Adverse Device Effect (ASADE)

A serious adverse device effect, which by its nature, incidence, severity or outcome has been previously identified in the risk analysis report.

8.2 Procedure for Assessing, Recording and Reporting Adverse Events, Adverse Device Effects, Serious Adverse Events and Serious Adverse Device Effects:

Safety surveillance within this study and the safety reporting both performed by the Investigator, starts as soon as the subject is enrolled in this study (date of signature of the informed consent). The Investigators who agree to participate in this observational study shall be instructed to report all adverse events on enrolled patients starting from the date of implant.

The safety surveillance and the safety reporting will continue until the last follow-up visit has been performed, the subject is deceased, the subject/investigator concludes his participation into the study or the subject/investigator withdraws the subject from the study.

Adverse event data including deaths will be collected throughout the clinical study and will be reported to the Sponsor on a dedicated case report form or through the EDC system. The Investigator will record all adverse events on the appropriate case report forms.

Records relating to the subject's subsequent medical course must be maintained and submitted (as applicable) to the Sponsor until the event has subsided or, in case of permanent impairment, until the event stabilizes and the overall clinical outcome has been ascertained. Adverse events will be monitored until they are adequately resolved. The status of the subject's condition should be documented at each visit.

Reportable adverse events to the Sponsor are considered:

- Adverse Device Effects (ADEs) which include device and/or procedure related events. All ADEs will be collected from the time of device implant.
- Serious Adverse Events (whether or not the event is considered device and/or procedure related). All SAEs will be collected from the time of device implant.

All above events will be reported to the Sponsor, as soon as possible, but no later than 72 hours of first learning of the event. In case of EDC failure, notify the Sponsor via [contact].

Additional information may be requested, when required, by the Sponsor in order to support the reporting of AEs to regulatory authorities.

Study Name: BRADYCARE II

Ver. A

CIP

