12.0 STATISTICAL CONSIDERATIONS

12.1 Statistical Design, Hypotheses, Method and Analytical Procedures

This is a post market, prospective, non-randomized observational study.

The primary endpoint will be summarized as counts and proportion of patients who experience complications. The 95% Binomial confidence interval for the complication rate at 1 year post implant will be reported as well.

Other data will be presented using appropriate summary statistics. All continuous data will be summarized using descriptive statistics, such as the number of non-missing data, mean ± standard deviation, median and range (minimum – maximum). Categorical data will be tabulated with counts and its percentage.

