12.8 Procedures that Take into Account All the Data

All subjects who have signed a Patient Informed Consent (PIC) will be considered enrolled in the study, hence are eligible for the primary analysis. Primary analysis population will include those subjects that have signed a PIC form, and have the CIP defined pacemaker implanted.

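### Section 6.8 lets safety status decide which ineligible subjects lose follow-up, while 12.8 keeps those with consent and the CIP-defined pacemaker in the primary analysis; the likely bias is small

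*Combined protocol and SAP*

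**What the plan says.** Section 6.8 opens its list of withdrawal reasons with "Reasons for subject's withdrawal include, but are not limited to". One entry has two parts: "Subject does not meet the inclusion/exclusion criteria and does not require additional follow-up for safety reasons". The same section also gives a general discretion: "The Investigator may decide to withdraw a subject from the study at any time with reasonable rationale".

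Section 8.2 runs safety surveillance and reporting until the last visit, death, or the point at which "the subject/investigator concludes his participation into the study or the subject/investigator withdraws the subject from the study". Complications after withdrawal are therefore not collected.

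Section 12.8 sets the analysis set: "Primary analysis population will include those subjects that have signed a PIC form, and have the CIP defined pacemaker implanted". It attaches no condition on eligibility or on completed follow-up. Section 12.1 adds: "The primary endpoint will be summarized as counts and proportion of patients who experience complications". A binomial 95% interval goes with that proportion. Section 12.9 allows no imputation outside questionnaire guidelines. No section says how a subject withdrawn before 1 year is counted.

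Section 6.3 says of a person who fails the criteria that "the subject cannot participate in the study and cannot be enrolled". Under section 4.7.2, however, enrollment happens at written consent. The 6.8 entry therefore matters for subjects whose ineligibility comes to light after consent.

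**The concern.** Take a subject who consented on day 35 after implant. The 30-day criterion in 4.6.1 is failed, but consent is signed and the CIP-defined pacemaker is in place, so 12.8 counts this subject. If the error is found later and the subject is well, the 6.8 entry fits and data collection stops. If the subject needs further safety follow-up, the entry does not fit. Observation time in this group can then depend on something close to the primary outcome.

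What is at stake is a small bias in the only primary estimate, with a direction that the plan leaves open. Withdrawn subjects kept in a crude proportion count as complication-free even if a complication follows. Withdrawn subjects who are dropped take mostly event-free people out of the denominator.

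Withdrawal gains little in return. The study is observational and the devices are already implanted and market-approved (sections 2.0 and 5.1), so no study treatment is stopped.

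**Working it through.** **The plan's own figures (section 12.2).** With p = 0.122, full width w = 0.031 and z = 1.96:

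n = 4z²p(1-p)/w² = 4 × 1.96² × 0.122 × 0.878 / 0.031² = 1712.7, rounded up to 1713.

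1713 / 0.85 = 2015.3, rounded up to 2016.

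Both figures reproduce, and this point does not affect them. The planned half-width is 3.1 / 2 = 1.55 points.

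**Inputs for the bias.**
- p = 12.2% (section 12.2), taken as the true rate for eligible and ineligible subjects alike (assumption).
- N = 2016 (section 12.2).
- f = share found ineligible after consent while holding the CIP-defined pacemaker. It is not in the documents. Assumed 1% to 5%, that is about 20 to 101 subjects.
- g = share of 1-year complications in these subjects that occur before the finding. It is not in the documents. Assumed 0.25 to 1.
- Strongest version of the mechanism: an ineligible subject is withdrawn if, and only if, complication-free when found. All other attrition is ignored.

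**Formulas.**
- Observed complications per enrolled subject: (1-f)p + fgp.
- Kept in the denominator: rate = (1-f)p + fgp.
- Dropped: rate = [(1-f)p + fgp] / [(1-f) + fgp].

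**Worked corners at f = 5%.**
- Kept, g = 0.25: 0.95 × 0.122 + 0.05 × 0.25 × 0.122 = 0.1174, a shift of -0.46 points. In subjects, 2016 × 0.05 × 0.122 × 0.75 = about 9 complications are missed, out of 2016 × 0.122 = 246.
- Dropped, g = 1: 0.122 / (0.95 + 0.0061) = 0.1276, a shift of +0.56 points.

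| f | g | Kept | Dropped |
|---|---|---|---|
| 1% | 0.25 | 12.11% (-0.09) | 12.23% (+0.03) |
| 1% | 0.5 | 12.14% (-0.06) | 12.25% (+0.05) |
| 1% | 1 | 12.20% (0) | 12.31% (+0.11) |
| 5% | 0.25 | 11.74% (-0.46) | 12.34% (+0.14) |
| 5% | 0.5 | 11.89% (-0.31) | 12.48% (+0.28) |
| 5% | 1 | 12.20% (0) | 12.76% (+0.56) |

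The two extremes cannot occur together. The largest downward shift needs late complications (low g), and the largest upward shift needs early ones (high g).

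**How much ineligibility would matter.** A shift equal to the half-width needs f of about 13% (dropped, g = 1) or about 17% (kept, g = 0.25).

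**Check by simulation.** With 10% found ineligible at a uniformly distributed time, a constant hazard and a true rate of 12.2%, the crude proportion was 11.6%. Dropping the withdrawn subjects gave 12.8%. A Kaplan-Meier estimate censoring at withdrawal gave 12.2%. That last result holds because the finding of ineligibility was simulated as unrelated to later risk.

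**The case against.** Three stronger readings are tempting, and the documents do not support them.

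- A reader might infer that ineligible subjects leave only when they have had no complication. The list is open and the investigator may withdraw anyone with a rationale. The entry speaks of a need for safety follow-up, which is undefined and is not the same as a past complication: a resolved complication may need none. An adverse event can also lead to withdrawal, since 6.8 provides for it: "When subject withdrawal from the clinical study is due to an adverse event the subject will be followed by their study doctor". That runs the other way.
- A reader might infer that 12.8 keeps every ineligible subject. It does not keep those without the CIP-defined pacemaker.
- A reader might infer that retaining subjects with complications inflates the rate. They are already cases, because 8.2 collects reportable events from implant. The bias comes only from withdrawn event-free subjects, and it is upward only if those subjects are dropped, which no section says.

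The case against goes further. There are four inclusion criteria and one exclusion, screening comes before enrollment, and the 30-day limit can be checked from two dates, so few subjects should be affected. The larger gap is the absence of any counting rule for subjects without 1-year follow-up: the 15% attrition allowance is 2016 - 1713 = 303 subjects. A time-to-event estimate would largely absorb the present issue if ineligibility is unrelated to later risk. Section 7.2 also presents the eligibility criteria as protecting subjects, and following ineligible subjects sits awkwardly with 6.3.

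Most of this stands and sets the severity. It does not remove the point: 6.8 and 8.2 let data collection stop, by safety status, on subjects whom 12.8 requires in the analysis. The tension with 6.3 is a reason to clarify that section as part of the change.

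**Conclusion.** The point holds with low severity. Among subjects found ineligible after consent who have the CIP-defined pacemaker, the listed withdrawal reason can make follow-up depend on safety status, which is plausibly but not demonstrably related to the primary outcome. On the literal reading of 12.8 the complication rate is slightly too low; if withdrawn subjects are dropped, it is slightly too high.

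The ranges are 0 to -0.46 points (kept) and +0.03 to +0.56 points (dropped). They rest on assumed values of f and g, equal risk in ineligible subjects, and the strongest form of the selection. Actual practice under an open list and investigator discretion could be less selective. Even the largest shift is about a third of the planned half-width (0.56 / 1.55 = 0.36).

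**What to change.** Replace the 6.8 entry with a rule on these lines: a consented subject with the CIP-defined pacemaker who is later found ineligible is recorded as a deviation and followed to the 12-month visit regardless of events. The exceptions are that consent is withdrawn or invalid, or that the investigator ends participation for another reason listed in 6.8.

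In 6.3, clarify that the bar on participation applies to ineligibility identified before enrollment. Leave 12.8 as it is, so that these subjects stay in the primary population and those without the CIP-defined pacemaker stay outside it.

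The cost is a short amendment to two sections. The downside is that a few deviating subjects complete routine visits they would otherwise have skipped as study visits. Because the list stays open and discretion remains, the change reduces selective withdrawal but cannot exclude it.
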